5.3. Multicentre Studies

This is a single centre study.

5.4. Examination of Covariates, Other Strata and Subgroups

5.4.1. Covariates and Other Strata

The list of covariates and other strata may be used in descriptive summaries and statistical analyses, some of which may also be used for subgroup analyses.

Category	Details
Strata	Time of Assessment (AM or PM)
Covariates	Baseline (of the analysis variable of interest), Study Period

5.5. Multiple Comparisons and Multiplicity

There are no planned adjustments for multiple comparisons or multiplicity.

5.6. Other Considerations for Data Analyses and Data Handling Conventions

Other considerations for data analyses and data handling conventions are outlined in the appendices:

Section	Component
12.3	Appendix 3: Assessment Windows

Section	Component
12.4	Appendix 4 : Study Phases and Treatment Emergent Adverse Events
12.5	Appendix 5 : Data Display Standards & Handling Conventions
12.6	Appendix 6 : Derived and Transformed Data
12.7	Appendix 7 : Reporting Standards for Missing Data
12.8	Appendix 8 : Values of Potential Clinical Importance

6. STUDY POPULATION ANALYSES

6.1. Overview of Planned Study Population Analyses

The study population analyses will be based on the population specified in [Appendix 11: List of Data Displays](#), unless otherwise specified.

Study population analyses including analyses of participant's disposition, protocol deviations, demographic and baseline characteristics, prior and concomitant medications and exposure will be based on GSK Core Data Standards.

Details of the planned displays are presented in [Appendix 12: List of Data Displays](#).

7. PHARMACODYNAMIC ANALYSES

7.1. Primary PainCart Analyses

7.1.1. Endpoint / Variables

The primary endpoints are

- UVB heat pain detection (Celsius)
- Cold pressor time to intolerable pain threshold (seconds)
- Electrical pain tolerance threshold (mA) – single stimulus

7.1.2. Summary Measure

For each of the three endpoints, the Analysis Area Under the Curve (AAUC) of the Ratio to Baseline will be the primary summary measure. The PainCart assessments will be log transformed in order to calculate the log change from baseline result which will be used for the primary analysis, and back transformed to obtain the ratio to baseline result. As default, summaries of Change from Baseline will also be calculated. If modelling assumptions are invalidated, then the results will not be presented. Ratio to baseline and change from baseline will be measured at each day where the assessment was performed. The AAUC is calculated via the trapezoidal method and will be normalised. Further details are referenced in Section 12.6.3 Pharmacodynamic.

7.1.3. Population of Interest

The primary analyses will be based on the MITT population for the cold pressor time to intolerable pain and electrical pain tolerance endpoints, and on the UVB-MITT for the UVB heat pain detection endpoint, unless otherwise specified.

7.1.4. Strategy for Intercurrent (Post-Randomisation) Events

Intercurrent current events (ICE) are defined as:

- Early withdrawal from study due to Covid-19
- Early withdrawal from study not due to Covid-19
- Use of prohibited medications
- Early discontinuation of study drug
- Use of COVID-19 vaccinations.

The “Hypothetical” strategy will be applied to handle the “Early withdrawal from study due to Covid-19”, “Early withdrawal from study not due to Covid-19 and “Early discontinuation of study drug” in the analysis for all endpoints. For the “Early withdrawal from study due to Covid-19” ICE, this strategy attempts to estimate treatment effects had the Covid-19 ICE not occurred. With COVID-19, the likelihood of participants withdrawing from the study is increasing (e.g. closure of the site, participants advised not

to leave homes etc.) which makes the Hypothetical strategy reasonable. The “Use of prohibited medications” and “Use of COVID-19 vaccinations” ICEs will implement a “Treatment Policy” strategy. The strategy implies direct use of data irrespective of the occurrence of the intercurrent events. The “Treatment policy” strategy is the same as de facto type estimand.

7.1.5. Statistical Analyses / Methods

Details of the planned displays are provided in [Appendix 12](#): List of Data Displays and will be based on GSK data standards and statistical principles.

Unless otherwise specified, endpoints / variables defined in Section [7.1.1](#) will be summarised using descriptive statistics, graphically presented (where appropriate) and listed.

Table 2: Primary PainCart Analyses details which of the primary endpoints are to be analysed and/or summarised.

Table 2 Primary PainCart Analyses

Estimand	Endpoint	Summary*	Primary Analysis – Bayesian AAUC Mixed ANCOVA	Listing
UVB Heat Pain	Detection (UVB Skin)	Yes	Yes (AAUC 1-8 days)	Yes (Inc. AAUC)
Cold Pressor	Tolerance	Yes	Yes (AAUC 1-15 days)	Yes (Inc. AAUC and eVAS)
Electrical pain – single stimulus (Pre-Cold Pressor)	Tolerance	Yes	Yes (AAUC 1-15 days)	Yes (Inc. AAUC and eVAS)

*The summary will include summary statistics for the summary measures, AAUC and post-test eVAS scores.

MMRM: Mixed Model Repeated Measures; ANCOVA: Analysis of Covariance; AAUC: Analysis Area Under Curve, BRM: Bayesian Repeated Measures

7.1.5.1. Statistical Methodology Specification

7.1.5.1.1. UVB heat pain detection (Celsius)

Endpoint / Variables

 Ratio to baseline (or change from baseline) in UVB heat pain detection (Celsius) AAUC(1-8 Days) If ratio to baseline is deemed suitable due to the distribution of the parameters, the response will be log transformed. Any transformation of a response variable is also expected to be applied to the corresponding baseline variable. Final decisions on transformations will be based on the observed data and model diagnostics
Model Specification

The analysis will be performed on the AAUC (1-8 days) using a Bayesian Mixed Analysis of Covariance (ANCOVA) model.
 
Refer to Section 12.6.3 Pharmacodynamic for the derivation of the AAUC via the trapezoidal method.
 
Non-informative priors will be utilized for each model parameter as either a normal distribution with a mean = 0 and variance = 1e6 (very large variance), unless specified elsewhere.
 
The prior for the variance covariance matrix will follow an inverse Wishart distribution. An inverse Wishart prior on the covariance matrix is chosen as it ensures sampling efficiency with PROC MCMC using the conjugate sampler to draw the unstructured covariance.
 
The random seed to use has been calculated prior to unblinding. Section 12.6 details the seed to use for the analyses in this RAP.
 
The mixed model ANCOVA will be fitted using Bayesian techniques with PROC MCMC using the following approach:
 
 Assume equal variances across treatment arms and use a pooled estimate of residual variability. Fit the following model: 
 M: Intercept + Treatment + Time of Assessment Stratum + Subject Level Baseline + Period Level Baseline + Study Period + Study Period*Period Level Baseline + Treatment*Study Period Time of assessment stratum (AM, PM) may be removed from the model if model convergence issues arise. For the model, use appropriate combinations of the model parameters (back transforming the combination if response variable is ratio to baseline) to obtain posterior distributions for the variables of interest. Binary flag variables can be used to evaluate the probability statements.


 The MCMC iterations are flagged if the posterior summary ratio > X, where X is various criteria. The posterior probability is then calculated by summarising the number of flagged MCMC iterations / total number of MCMC iterations.
Model Checking & Diagnostics

 Refer to the relevant documentation (Bayesian Statistics Best Practice at GSK – Clinical Trials using Bayesian Inference).
Model Results Presentation

 The posterior ratio to baseline AAUC median for each treatment group will be presented along with the coefficient of variation (CV) (%) (calculated as $\sqrt{\exp(sd^2) - 1}$) and/or 95% credible intervals (Crl). The posterior treatment ratio to placebo, along with corresponding 95% Credible Intervals (Crl) and posterior probabilities that the true ratio is greater than 1 will be presented. If the Ratio to Baseline is not suitable, the change from baseline AAUC in UVB heat pain detection will be compared between the treatment groups using a Bayesian mixed ANCOVA with the same model specification as above. All available post-baseline scheduled visits will be included in the analysis. Non-informative priors will be used for all modelling parameters. Wherever possible conjugate priors will be utilised. An unstructured covariance matrix will be used to model the within-subject error.

7.1.5.1.2. Cold pressor time to intolerable pain & Electrical pain tolerance threshold – single stimulus

Endpoint / Variables

 Ratio to baseline in cold pressor time to intolerable pain threshold (seconds) (AAUC 1-15 days) Ratio to baseline in electrical pain tolerance threshold (mA) – single stimulus (AAUC 1-15 days) If ratio to baseline is deemed suitable due to the distribution of the parameters, the response will be log transformed. Any transformation of a response variable is also expected to be applied to the corresponding baseline variable. Final decisions on transformations will be based on the observed data and model diagnostics
Model Specification

 A Bayesian mixed ANCOVA model will be fitted to the ratio to baseline AAUC (1-15 days) for the electrical pain tolerance threshold endpoint and cold pressor time to intolerable pain endpoint, and used to estimate the ratio to placebo. Refer to Section 7.1.5.1.1 Model Specification for more information
Model Checking & Diagnostics

 Refer to Section 7.1.5.1.1 Model Checking & Diagnostics for more information

Model Results Presentation	

 Refer to Section 7.1.5.1.1 Model Results Presentation for more information 	
Interim Analysis 1	

 The first interim analysis may occur once the final UVB-MITT participant in period 3 has completed their day 15 assessments of the PainCart tests. In addition to posterior probabilities, predictive probabilities of achieving the criteria of interest at the end of the study if we were to randomise and analyse an additional 12 subjects will be estimated using a Bayesian Normal-Normal update. Vague priors for all modelling parameters will be used to compute the posterior distributions. Further information is contained in the 209973 Interim Analysis Charter. 	

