9.2. Sample Size Determination

A maximum of 30 participants will be randomized into the study as per Section 6.3.1 such that approximately 24 participants complete all three periods of the study (except UVB assessments on irradiated skin). Approximately 18 subjects will undergo the UVB assessments on irradiated skin such that approximately 15 subjects complete the UVB assessments in all three periods.

On each of the three endpoints, a positive conclusion will be declared if, given the data, there is at least 90% probability that the ratio vs placebo is better than 1 (no difference) and a negative conclusion will be declared if, given the data, there is less than 75% probability that the difference vs placebo is better than 1 (no difference).

The coefficient of variation for each endpoint was estimated from [Loudon, 2018](#); [Okkerse, 2017](#); [Siebenga, 2019](#); [van Amerongen, 2018](#), and is shown in [Table 1](#).

Table 1 Coefficient of Variability

UVB heat pain detection (°C)	Cold pressor time to intolerable pain threshold (sec)	Electrical pain tolerance threshold (mA)
3.7%	25.6%	19.1%

With 24 completed participants using a three-period two-treatment incomplete-block crossover design, the probability of declaring a positive outcome on each endpoint where there is no improvement is fixed at 10% by definition (Type I Error). The operating characteristics of each endpoint is provided in [Figure 4](#).

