9.2.1. Sample Size Sensitivity

The impact of increases/decreases in the variability of each endpoint from the expected variability is demonstrated in [Figure 4](#) and [Figure 5](#). Subject drop out of 20% is accounted for in the sample size. Operating characteristics and probability of positive outcomes [Figure 4](#) and [Figure 5](#) are based on a sample size of 24 for Electrical pain tolerance and Cold pressor time to intolerable pain threshold, and sample size of 15 for UVB heat pain detection on irradiated skin.

Figure 4 Operating Characteristics of Study Design. a: Electrical pain tolerance threshold (mA) b: Cold pressor time to intolerable pain threshold (sec) c: UVB heat pain detection ($^{\circ}\text{C}$)

[figure not shown]
[figure not shown]

Figure 5 Probability of positive conclusion based on different assumptions.
a: Electrical pain tolerance threshold (mA) **b:** Cold pressor time to intolerable pain threshold (sec) : UVB heat pain detection (°C)

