3. PLANNED ANALYSES

3.1. Interim Analyses

Two interim analyses of the primary endpoints to inform internal decision making may be conducted during the study. The interim analyses may occur when:

- The final UVB-MITT participant (approx. 15 evaluable participants) to have completed the day 15 assessments of the PainCart assessments in study period 3 (final study period).
- The final randomised participant has completed the day 15 assessments of the PainCart assessments in study period 3 (final study period).

The table below details the endpoints that will be analysed/summarised at the interim:

Purpose of Interim	Endpoints
Interim Analysis 1 (Futility)	
UVB heat pain detection (Celsius)
 
 • Absolute values (Summarised) • Change from baseline (Summarised) • Ratio to Baseline (Summarised) • AAUC of Ratio to Baseline (Analysed) 
Cold pressor time to intolerable pain threshold (seconds):
 
 • Absolute values (Summarised) • Change from baseline (Summarised) • Ratio to Baseline (Summarised) • AAUC of Ratio to Baseline (Analysed) 
Electrical pain tolerance – single stimulus (mA):
 
 • Absolute values (Summarised) • Change from baseline (Summarised) • Ratio to Baseline (Summarised) • AAUC of Ratio to Baseline (Analysed) 
Summary of Demographic Characteristics
 
Summary of Derived Serum GSK3858279 Pharmacokinetic Parameters (non-transformed and log-transformed)
 
Summary of Serum GSK3858279 Concentration-Time Data (ng/mL)
 
Summary of Derived Free and Total CCL17 in Serum Target Engagement Parameters (non-transformed and log-transformed)

	
Summary of Free & Total CCL17 in Serum Concentration-Time Data (pg/mL).
 
Summary of All Adverse Events by System Organ Class and Preferred Term by Period (>=2 Subjects with the AE)

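### Does projecting 12 further analysed subjects at interim 1, with no dropout, distort the futility decision?

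*SAP*

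**What the plan says.** The relevant statements are spread over both documents.

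- SAP Section 7.1.5.1.2 (Interim Analysis 1) says that, besides posterior probabilities, the chance of meeting the criteria at the end of the study "if we were to randomise and analyse an additional 12 subjects will be estimated using a Bayesian Normal-Normal update". It refers to the Interim Analysis Charter for details.
- SAP Section 3.1 times this look by "The final UVB-MITT participant (approx. 15 evaluable participants" finishing Day 15 of period 3.
- Protocol Section 9.2 sets the overall size: "A maximum of 30 participants will be randomized into the study as per Section 6.3.1 such that approximately 24 participants complete all three periods". For the UVB subset: "Approximately 18 subjects will undergo the UVB assessments on irradiated skin such that approximately 15 subjects complete the UVB assessments in all three periods".
- Protocol Section 9.2.1 adds "Subject drop out of 20% is accounted for in the sample size", and says that the operating characteristics "are based on a sample size of 24 for Electrical pain tolerance and Cold pressor time to intolerable pain threshold".
- Protocol Section 9.2 calls an endpoint positive when "there is at least 90% probability that the ratio vs placebo is better than 1 (no difference".
- Protocol Section 9.5 names cold pressor tolerance and single-stimulus electrical tolerance as the endpoints on which the study could stop. SAP Section 7.1.3 analyses both in the MITT population, which SAP Section 4 defines by at least one PainCart assessment in at least two periods.
- SAP Section 1.1, in the entry for RAP Amendment 1, records that the study stopped because the futility threshold was not met.

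**The concern.** Dropout appears to be counted once and then forgotten. Of about 18 UVB participants, about 15 are expected to be evaluable at the interim, so losses are allowed for there. The next 12 are projected as both randomised and analysed, with no losses. The implied final size is 27, although the protocol bases the operating characteristics of these endpoints on 24.

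The direction matters. When the interim result is weak, more projected data gives it more room to recover. A predictive probability computed with too many future subjects is then too high, and a rule that stops below a fixed value is triggered less often. If the drug does nothing, healthy participants could be dosed and irradiated for longer than the planned final size would justify.

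**Working it through.** **Where 12 comes from.** Completers inflated for dropout: 24 / (1 − 0.20) = 30, as stated. Slots left after the UVB subset: 30 − 18 = 12. The SAP's figure is therefore the randomised remainder.

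**How many of the 12 would contribute.** Several readings are possible:

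- 24 − 15 = 9 three-period completers;
- 12 × 0.80 = 9.6 at the stated dropout rate;
- 12 × 15/18 = 10 at the rate implied by the UVB subset;
- about 11.4 effective subjects if all expected dropouts leave after period 2.

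The last figure follows from the MITT definition. Under the sequences in SAP Section 5.1 (A/P/P and P/A/A), a subject who leaves after period 2 has had both treatments. Ignoring period terms, the within-subject contrast has variance (1 + 1)σ² = 2σ² with two periods and (1 + ½)σ² = 1.5σ² with three. Such a subject carries 1.5/2 = 75% of the full information, so 9.6 + 2.4 × 0.75 = 11.4.

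**Predictive probability.** Assumptions: vague prior, known variance, information proportional to the number of subjects. With n₁ subjects at the interim, n₂ to come, interim statistic z and success at a posterior of at least 90% (normal quantile 1.2816):

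PP = Φ[(z·√(n₁ + n₂) − 1.2816·√n₁) / √n₂]

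At z = 0 and n₁ = 15:

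- n₂ = 12: Φ(−1.2816 × √(15/12)) = Φ(−1.433) = 7.6%
- n₂ = 9: Φ(−1.2816 × √(15/9)) = Φ(−1.655) = 4.9%

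| Interim posterior Pr(ratio > 1) | n₂ = 12 | n₂ = 9.6 | n₂ = 9 | 12 minus 9 (points) |
|---|---|---|---|---|
| 50% | 7.6% | 5.5% | 4.9% | 2.7 |
| 60% | 14.6% | 11.6% | 10.7% | 3.9 |
| 70% | 25.9% | 22.3% | 21.2% | 4.7 |
| 75% | 33.7% | 30.1% | 29.0% | 4.7 |
| 80% | 43.2% | 39.9% | 39.0% | 4.3 |
| 90% | 68.8% | 67.3% | 66.9% | 1.8 |
| 95% | 85.0% | 84.9% | 84.9% | 0.1 |
| 97.5% | 93.4% | 93.8% | 93.9% | −0.5 |

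The largest gap from 12 is 4.7 points for 9, 3.6 for 9.6 and 0.8 for 11.4. The sign changes at z = 1.67 (posterior 95.2%), where the predictive probability is about 86%. With n₁ = 18 the largest gap between 12 and 9 is 4.8 points.

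**Chance of stopping an inactive drug.** The cut-off is in the charter, so a range is assumed. For cut-off g the boundary is z = (1.2816·√n₁ + Φ⁻¹(g)·√n₂)/√(n₁ + n₂), and the stopping rate under no effect is Φ of that value. For g = 10% and n₁ = 15, z is 0.101 with n₂ = 12 and 0.228 with n₂ = 9.

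| Assumed cut-off | n₂ = 12 | n₂ = 11.4 | n₂ = 9 |
|---|---|---|---|
| 5% | 44.4% | 45.4% | 50.2% |
| 10% | 54.0% | 54.9% | 59.0% |
| 20% | 65.3% | 66.0% | 69.1% |
| 30% | 72.8% | 73.3% | 75.6% |
| 50% | 83.0% | 83.3% | 84.5% |

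Against 9, the loss runs from 5.8 points (50.2 − 44.4) down to 1.5 (84.5 − 83.0). Against 11.4 it is 1.0 point or less.

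**The case for a change.** The strongest case for changing the text is that nothing in the documents reconciles 12 with 24. Full information from 12 further subjects needs zero attrition, and even the most generous reading gives 11.4. Replacement is permitted but optional, and 18 + 12 already fills the cap of 30. The reported predictive probability then describes a 27-subject analysis that the protocol does not plan, and stating the expected number would cost one line. All of that stands as a description.

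It does not carry the stronger claim that the right number is about 9 and that futility is under-triggered.

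- Nine counts three-period completers. SAP Section 2.1 drops the Completers population and uses MITT, so writing 9 would put the bottom of the range in place of the top.
- The interim number is itself approximate. Fifteen refers to UVB participants, and the documents do not say whether any non-UVB participants would also contribute cold pressor and electrical data by then.
- The SAP sentence is conditional. It describes a full-follow-up scenario and does not forecast retention.
- A cut-off chosen with 12 in mind would already absorb the shift. The documents also do not say whether the threshold applies to the predictive or the posterior probability; on the posterior, the 12 plays no part.

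**Conclusion.** The mismatch is genuine and minor, and correcting it gains nothing. Twelve is a no-dropout projection. It raises the predictive probability for weak interim results by at most 0.8 to 4.7 points, depending on whether 11.4 or 9 effective subjects is the fair comparison. Under no effect and assumed cut-offs of 5% to 50%, the chance of stopping falls by between 0.3 and 5.8 points.

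What settles the matter is the SAP's own history. The look has been taken and the study stopped for futility, even though any bias from the 12 worked against stopping. If the rule used the predictive probability, a smaller projected number would have lowered it, unless it stood above about 86%, which is not a plausible place for a futility cut-off. The decision would therefore have been the same. With the study stopped, the hypothetical 12 subjects play no part in the final posterior probabilities, so the conclusions are unaffected too.

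This rests on about 15 subjects at the interim (18 gives similar figures), a vague prior, known variance and information proportional to the number of subjects. The charter, which holds the cut-off, is not among the documents. An analyst reporting the interim result need only describe the 12 as the case with no further dropout.

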7.2. Exploratory PainCart Analyses

7.2.1. Endpoint / Variables

The exploratory endpoints are:

- Cold pressor time to pain detection threshold
- Electrical pain detection threshold– single stimulus
- Electrical pain tolerance threshold– repeat stimulus
- Electrical pain detection threshold– repeat stimulus
- Conditioned pain modulation (CPM) detection threshold
- Conditioned pain modulation (CPM) tolerance threshold
- Heat pain detection on normal skin
- Pressure pain tolerance threshold
- Pressure pain detection threshold

7.2.2. Summary Measure

For each of the exploratory PainCart endpoints apart from heat pain detection on normal skin, conditioned pain modulation and pressure pain thresholds, Ratio to Baseline will be the primary summary measure. As default, summaries of Change from Baseline will also be shown. For the conditioned pain modulation endpoint, the change from baseline will be the summary measure. If modelling assumptions are invalidated, then neither ratio to/change from baseline may be shown. For heat pain detection on normal skin and pressure pain thresholds only summary statistics (mean/geometric mean, SD/CV(%), Median, Min, Max) will be produced. Refer to [Table 4](#) for further details.

7.2.3. Population of Interest

The exploratory analyses will be based on the MITT population, unless otherwise specified.

